8.7. Data analysis

The detailed methodology for data analysis will be described in the Statistical Analysis Plan (SAP).

As a first step, extracted patients will be divided into two cohorts, primary prevention cohort and secondary prevention cohort based on the previous diagnosis of stroke. Clinical and demographic characteristics will be compared with two cohorts at baseline and on the index date (date of the initiation of warfarin and apixaban) and incidence rates of stroke/SE and major bleeding per 1,000 person-years will be calculated during follow-up period. In addition, interaction analysis will be conducted to investigate an interaction between OAC (warfarin/apixaban) and presence or absence of the previous episode of stroke.

- As a second step, only secondary prevention cohort will be used for further analyses as follows, Crude (before IPTW) patient characteristics are compared between warfarin and apixaban cohorts using appropriate methods (continuous variables: unpaired t-test or Mann-Whitney U-test, categorical variables: chi-square test)
- A propensity score is calculated based on multinomial logistic regressions in order to account for confounding effects and to ensure that patient characteristics are balanced between the warfarin cohort and apixaban cohort. An inverse probability of treatment weighting (IPTW) method using the calculated propensity score will be applied. To avoid sample size inflation and to ensure appropriate estimation of variances, s-IPTW (stabilized IPTW) is used here.
- Balanced (after IPTW) patient clinical and demographic characteristics are shown. Covariate balance between apixaban and warfarin cohorts after s-IPTW is assessed in terms of the standardized differences with a threshold of 0.1
- Kaplan Meier curves of balanced cohorts for each endpoint are drawn.
- Incidence rates of endpoints are calculated and shown per 1000 person-years.
- Hazard ratios with 95% confidence intervals will be calculated using a Cox proportional hazards regression model that incorporate only the index OACs as independent variables.

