### 5.4. COVARIATES

Variable	Role	Operational definition
Previous stroke		
Previous incidence of stroke	Patient characteristic:	
Previous incidence of TIA	Patient characteristic:	Defined elsewhere using ICD-10 codes

PFIZER CONFIDENTIAL

Types of previous stroke	Patient characteristic:	cardioembolic stroke or cerebral infarction
Treatment status	Patient characteristic:	Inpatients or outpatients
Hospitalization days	Patient characteristic:	0 or days in hospital
NVAF diagnosis and treatment		
Year	Patient characteristic	Year first diagnosed with NVAF
Anticoagulant	Patient characteristic	Warfarin or apixaban
Patients		
age	Patient characteristics on index date	Years
Age category	Patient characteristics on index date	
age $\leq 65$		
age $65 < , \leq 75$		
age $75 <$		
Gender category	Patient characteristics on index date	Male or female
Body weight	Baseline characteristic	Kg (if available)
Height	Baseline characteristic	cm (if available)
BMI	Baseline characteristic	Calculated from body weight and height using a formula of (weight [kg]) / (height [m]) 
Comorbidity profile		
Chronic obstructive pulmonary disease (COPD)	Baseline characteristic	Defined elsewhere using ICD-10 codes
Congestive heart disease	Baseline characteristic	Defined elsewhere using ICD-10 codes
Ischemic heart/coronary artery disease	Baseline characteristic	Defined elsewhere using ICD-10 codes
Diabetes	Baseline characteristic	Defined elsewhere using ICD-10 codes
Hyperlipidemia	Baseline characteristic	Defined elsewhere using ICD-10 codes
Hypertension	Baseline characteristic	Defined elsewhere using ICD-10 codes
Liver disease	Baseline characteristic	Defined elsewhere using ICD-10 codes
Renal disease	Baseline characteristic	Defined elsewhere using ICD-10 codes
Peripheral vascular disease	Baseline characteristic	Defined elsewhere using ICD-10 codes
Pregnancy	Exclusion criteria	Presence of "pregnancy"-related ICD-10 codes.

PFIZER CONFIDENTIAL

Cancer	Baseline characteristic	Defined elsewhere using ICD-10 codes
VTE	Baseline characteristic (exclusion criteria)	Defined elsewhere using ICD-10 codes
Medicines		
Anti-hypertensive drugs	Baseline characteristic	Defined elsewhere using drug codes
Anti-platelet drugs	Baseline characteristic	Defined elsewhere using drug codes
NSAIDs (chronic use*)	Baseline characteristic	Defined elsewhere using drug codes
Statins	Baseline characteristic	Defined elsewhere using drug codes
Outcomes		

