#### 7.1.2. Patient characteristic balancing

[figure not shown]
In this study, matched cohorts (warfarin cohort versus apixaban cohort) will be created. A propensity score will be calculated based on multivariable logistic regressions in order to account for confounding effects\* and to ensure that patient characteristics will be balanced between the warfarin cohort and apixaban cohort. An inverse probability of treatment weighting (IPTW) method using the calculated propensity score will be applied. To avoid sample size inflation and to ensure appropriate estimation of variances, s-IPTW (stabilized IPTW) is used here.

Balanced (after IPTW) patient clinical and demographic characteristics will be shown. Covariate balance between apixaban and warfarin cohorts after s-IPTW will be assessed in terms of the standardized differences with a threshold of 0.1. We will present the data for each variables and standardized differences in the same table side by side to ensure that two cohorts are balanced after IPTW.

\* Covariates used for the calculation of propensity score

- Gender: male or female
- Age: absolute years
- BMI: categories BMI (kg/m^2) (<18, 18 to <22, 22 to <25, 25+, missing)
- CHADS2 score: absolute score, categories (0, 1, 2, 3, 4, 5, 6)

PFIZER CONFIDENTIAL

[figure not shown]

- CHA2DS2-VASc: absolute score, categories (0, 1, 2, 3, 4, 5, 6, 7, 8, 9)
- Treatment status of the most recent stroke before the index date (outpatient treatment, inpatient treatment, missing)
- mRS (modified Rankin Scale) at time of admission due to most recent stroke (0,1,2,3,4,5, missing)
- JCS (Japan coma scale) at time of admission due to most recent stroke (I, II, III, missing)
- ADL (Activities of daily living) at time of admission due to most recent stroke (0-19, 20-39, 40-59, 60-79, 80-100, missing)
- Duration of hospitalization due to most recent stroke
- Destination after discharge from hospitalization due to most recent stroke (1 or 5 or other (2,3,4,6,7,8,9))
- Use of tPA or urokinase for treatment of most recent ischemic stroke (thrombolytic therapy)
- Type of most recent stroke stroke (TIA, ischemic stroke, cerebral bleeding, cardiogenic thromboembolism, unknown/others)
- 

*Note: in patients with a medical history of incidence multiple stroke events, only information regarding most recent stroke (i.e., stroke event closest to the index date) will be used.*

- Comorbidities
  - Hypertension
  - Heart failure in baseline

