  - Coronary heart disease in baseline
  - Peripheral arterial disorder in baseline
  - History of myocardial infarction
  - Hyperthyroidism or thyrotoxicosis in baseline
  - Diabetes in baseline
  - Liver diseases in baseline
  - Diabetes mellitus diagnosis in baseline
  - Cancer diagnosis in baseline
  - Dementia in baseline
  - Renal diseases in baseline
  - Gastrointestinal ulcer in baseline

PFIZER CONFIDENTIAL

- History of bleeding
- Medicines
  - Treated with antiplatelet drug in baseline
  - Treated with NSAIDs in baseline
  - Treated with anti-hypertensives in baseline
  - Treated with anti-arrhythmics in baseline
  - Treated with beta-blockers in baseline
  - Treated with heparins in baseline
- Others
  - Cardioversion
  - Cardiac ablation

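### Statins, hyperlipidemia and COPD are planned baseline characteristics but are missing from the propensity-score list, so the weighting does not target their balance, and the two documents disagree on Cox covariates

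*SAP*

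**What the plan says.** SAP 5.4 has rows reading "Statins Baseline characteristic Defined elsewhere using drug codes" and "Hyperlipidemia Baseline characteristic Defined elsewhere using ICD-10 codes", and gives COPD the same role. Protocol Table 1 (section 8.3) has the same three rows.

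SAP 7.1.2 sets out the variables for the propensity model under "Covariates used for the calculation of propensity score". The medicines run from "Treated with antiplatelet drug in baseline" to "Treated with heparins in baseline", with NSAIDs, anti-hypertensives, anti-arrhythmics and beta-blockers between them. No lipid-lowering drug appears. The comorbidities include neither hyperlipidemia nor COPD, while diabetes is entered twice, the second time as "Diabetes mellitus diagnosis in baseline".

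For the outcome model, Protocol 8.7 specifies a "Cox proportional hazards regression model that incorporate only the index OACs as independent variables". In SAP 7.2.3, the covariate column of the Cox rows for the effectiveness and safety endpoints points to section 5.4.

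SAP 7.1.1 and 7.1.2 assess balance after weighting by standardized differences with a cutoff of 0.1. Neither section says what follows if the cutoff is exceeded.

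**The concern.** The comparison of apixaban with warfarin in secondary prevention relies on stabilized weights to remove confounding. A variable outside the propensity model is balanced only as far as it is correlated with variables inside it. If lipid treatment differs between users of the two drugs and is also related to recurrent stroke, part of that difference could pass into the primary hazard ratio. Both conditions are assumptions, since neither document states either one.

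The plan already collects these variables, so the exposure is avoidable. Protocol 8.9 names vital signs and laboratory values as absent from the score. A reader of that section would not learn that three collected variables are absent too. SAP 7.1.2 gives no reason for leaving them out.

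**Working it through.** **1. List comparison.** This covers the comorbidity and medicine blocks of SAP 5.4 against SAP 7.1.2.

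- Medicines: 5.4 has four classes. Anti-hypertensives, antiplatelets and NSAIDs have a counterpart in 7.1.2. Statins do not.
- Comorbidities whose role is baseline characteristic only: 5.4 has ten. Eight have a counterpart (heart failure, coronary disease, diabetes, hypertension, liver disease, renal disease, peripheral vascular disease, cancer). Hyperlipidemia and COPD do not.
- Pregnancy and VTE are exclusion items in 5.4, so there is nothing to balance.

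The lists differ in the other direction too. For example, 7.1.2 has dementia, gastrointestinal ulcer and heparins, which 5.4 lacks.

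**2. Whether a later step adjusts.** Under Protocol 8.7, no: the weighted model has one independent variable. Under SAP 7.2.3, perhaps: the endpoint Cox rows point to 5.4. That pointer cannot be carried out as written. Section 5.4 includes the outcomes themselves, the exclusion items and the anticoagulant, and the same entry stands against the incidence-rate and Kaplan-Meier rows, which have no regression covariates. The documents are therefore inconsistent on adjustment.

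**3. Possible size.** The plan gives no figure on this point. The sample-size table in SAP 7.2.2 does not depend on the propensity covariates and is unaffected. The only input from the documents is the anticipated hazard ratio of 0.65 (SAP 7.2.2). Assumed inputs are a statin rate ratio for stroke (RR) of 0.7 to 0.9 and statin use after weighting (p) that differs by 5, 10 or 20 percentage points.

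Bias factor = [1 + p_apixaban × (RR − 1)] / [1 + p_warfarin × (RR − 1)]

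Standardized difference = (p_apixaban − p_warfarin) / √{[p_apixaban(1 − p_apixaban) + p_warfarin(1 − p_warfarin)] / 2}

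Example with RR 0.7 and use of 25% (warfarin) and 45% (apixaban): (1 − 0.3 × 0.45) / (1 − 0.3 × 0.25) = 0.865 / 0.925 = 0.935. The standardized difference is 0.20 / √[(0.2475 + 0.1875) / 2] = 0.43. An observed 0.65 would then correspond to 0.65 / 0.935 = 0.695.

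| Use, warfarin / apixaban | Std. difference | RR | Bias factor | HR behind an observed 0.65 |
|---|---|---|---|---|
| 35% / 40% | 0.10 | 0.9 | 0.995 | 0.653 |
| 35% / 40% | 0.10 | 0.8 | 0.989 | 0.657 |
| 35% / 40% | 0.10 | 0.7 | 0.983 | 0.661 |
| 30% / 40% | 0.21 | 0.9 | 0.990 | 0.657 |
| 30% / 40% | 0.21 | 0.8 | 0.979 | 0.664 |
| 30% / 40% | 0.21 | 0.7 | 0.967 | 0.672 |
| 25% / 45% | 0.43 | 0.9 | 0.979 | 0.664 |
| 25% / 45% | 0.43 | 0.8 | 0.958 | 0.679 |
| 25% / 45% | 0.43 | 0.7 | 0.935 | 0.695 |

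If statins are more common with warfarin, the factors invert, to 1/0.995 = 1.005 up to 1/0.935 = 1.069. An observed 0.65 would then correspond to 0.647 down to 0.608.

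**4. Comparison with the E-value.** For a hazard ratio of 0.65, 1/0.65 = 1.538 and the E-value is 1.538 + √(1.538 × 0.538) = 2.45. The strongest assumed case has a ratio of use of 0.45/0.25 = 1.8 and an outcome ratio of 1/0.7 = 1.43. Both are below 2.45, so statins alone would not explain away 0.65.

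**The case against.** The strongest defence has four parts.

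- **Partial balance.** The propensity list holds coronary disease, myocardial infarction history, peripheral arterial disorder, diabetes, hypertension, antiplatelets, CHADS2, CHA2DS2-VASc and the type and treatment of the last stroke. Several plausibly track lipid treatment. This stands. A reader might infer from the omission that statin use will be unbalanced. The documents support only that its balance is not targeted.
- **Later adjustment.** A reader might infer from Protocol 8.7 that no later step can adjust for statins. SAP 7.2.3 prevents that conclusion, and Protocol 8.7 itself leaves detailed methods to the SAP. But the pointer to 5.4 is not a workable covariate list, so what it establishes is a conflict to resolve.
- **Visibility.** On a natural reading of SAP 7.1.1 and 7.1.2, standardized differences would be shown for statins as well. This stands in part. Displaying an imbalance does not correct it, and no remedy is stated.
- **Other safeguards.** SAP 7.2.1 plans E-values, and Protocol 8.9 acknowledges residual confounding. E-values address unmeasured confounders, whereas these variables are measured. The limitation does not mention them.

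The premise that lipid treatment bears on recurrence is also not in the documents. The case for adding the variables does not need it, because the plan itself designates them as baseline characteristics and uses the score to balance patient characteristics.

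**Conclusion.** The point holds as a gap in specification. Three collected baseline characteristics are outside the propensity model without a stated reason, no action is tied to the 0.1 threshold, and the protocol and SAP disagree on what enters the Cox model.

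The likely effect on the hazard ratio is small: a factor of about 0.94 to 0.995, or its inverse, under the assumed statin effects and residual differences in use. At a residual standardized difference near 0.10 the factor is 0.983 to 0.995. These figures describe statins only and take the stated gap as what remains after weighting. They are not estimates for this cohort.

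A reader might infer that the primary result is biased in apixaban's favour. The documents do not support that: they give neither statin use by drug nor its effect, and the direction reverses if use is higher with warfarin. The change is worth making because it costs almost nothing. The omission does not by itself put the primary comparison in doubt.

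**What to change.** - Add statins, hyperlipidemia and, for consistency with 5.4, COPD, each measured in the baseline period, to the SAP 7.1.2 propensity list.
- Apply the 0.1 standardized-difference check to every baseline characteristic in 5.4 as well as to the 7.1.2 variables. State that if any exceeds 0.1 after weighting, the propensity model is re-specified before outcomes are examined.
- Reconcile SAP 7.2.3 with Protocol 8.7. Either state that the weighted Cox model contains the index anticoagulant only, with 7.1.2 as the reference for confounder control, or name the covariates one by one.
- Delete the second diabetes line. This is editorial: if both lines denote the same variable, the redundant term leaves the fitted scores unchanged.

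The cost is three more terms in one logistic model, from variables the plan already collects, plus edits to SAP wording. The sample-size table does not change.

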13. LIST OF TABLES

Table1. Variables

Table2. Categories of clinical departments

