## 2.2. STUDY OBJECTIVES

*The pivotal randomized clinical trial, ARISTOTLE study, and other RWE, in which medical and claims data have been retrospectively analyzed, have shown that the risks of incidence of stroke + systemic embolism and major bleeding in patients with NVAF treated with apixaban is equal to or lessor than those in patients treated with warfarin. As mentioned above, patients with NVAF and with a history of ischemic stroke (that is, in secondary prevention) could be at higher risk of recurrence and bleeding. Although neurologists generally use direct oral anticoagulants (DOAC) for secondary prevention, a significant portion of the patients in secondary prevention are still treated with warfarin in Japan. The*

results of randomized trials have been indicated that apixaban is superior to warfarin in reducing the risk of recurrence and/or bleeding with secondary prevention of stroke. However, there is no clear evidence in Japanese patients with secondary prevention of stroke. The research question of this study is whether apixaban is associated with lower risk of stroke (ischemic and hemorrhagic) and bleeding compared to warfarin in higher-risk secondary prevention patients as well.

The purposes of this study are 1) to characterize the primary and secondary prevention patients, 2) to calculate incidence rates of stroke/SE or major bleeding in each cohort and 3) to investigate for Japanese secondary prevention patients as RWE on the effectiveness and safety of apixaban compared to warfarin in patients NVAF.

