#### **4.1.2. Exclusion criteria**

*Patients who meet the following exclusion criteria will be excluded from this study*

1. *Patients with a diagnosis of valvular AF (standard disease code: 8846941), postoperative AF (8847772), AF associated with mechanical valve malfunction (T82.0), mechanical complication of heart valve prosthesis (T82.0), or rheumatic AF (I05-I09) during the baseline period\*\*.*
2. *Patients with a diagnosis of VTE during the baseline period*
3. *Patients who are prescribed any anticoagulant during the baseline period.*
4. *Patients who are prescribed anticoagulants other than warfarin and apixaban on the index date*
5. *Patients who were hospitalized for more than 6 months (including index date) regardless of reason for hospitalization.*

*\*\*: maximally 6 months prior to the index date. If sufficient patient information is available for the analysis, patients who cannot have a 6-month baseline period will be included in the analysis.*

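### The propensity score records where the most recent stroke was treated, but not whether the anticoagulant was started in hospital or as an outpatient

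*SAP*

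**What the plan says.** **Propensity score.** SAP 7.1.2 lists sex, age, BMI, two stroke risk scores, features of the most recent stroke, comorbidities, bleeding history, medicines, and two procedures, ending with "Cardiac ablation". The one care-setting item is "Treatment status of the most recent stroke before the index date (outpatient treatment, inpatient treatment, missing". For patients with several strokes, "only information regarding most recent stroke (i.e., stroke event closest to the index date) will be used". The footnote to SAP 4.1.1 looks for that stroke back to the patient's first appearance in the database.

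**Other setting variable.** SAP 5.4 has a treatment-status variable defined as "Inpatients or outpatients". It stands under the previous-stroke heading, as does its counterpart in Protocol 8.3.

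**Who is kept.** SAP 4.1.2, item 5, excludes "Patients who were hospitalized for more than 6 months (including index date) regardless of reason for hospitalization". Protocol 8.2.2, item 5, instead excludes patients in continuous hospital stay because of a first stroke or another serious disease, with no time limit.

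**Endpoints.** SAP 5.1.1 counts a recurrent stroke only after the patient has been discharged, become an outpatient and been readmitted for stroke. SAP 5.2.1 restricts major bleeding to outpatients admitted for the bleed; a bleed during a stay does not count.

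**Outcome model.** Protocol 8.7 puts only the index anticoagulant in the Cox model.

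**The concern.** A patient started on a ward and a patient started in a clinic differ in two ways that bear on the primary results. Their prognosis may differ. Their opportunity to have a counted event also differs: under the endpoint rules the ward patient cannot have a counted stroke or major bleed until discharge, although follow-up runs from the index date. Start setting is therefore a plausible determinant of the recorded event rate. If it is also associated with the choice of drug, it confounds both primary hazard ratios.

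The variable is fixed at time zero. It should also be derivable, because SAP 2.1.2 says inpatient and outpatient records are linked for each patient and the endpoint definitions already need that status. This separates it from the unavailable items that Protocol 8.9 names, such as blood pressure, INR and renal function.

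**Working it through.** The plan gives no figure for in-hospital starts, so there is none to reproduce on this point. Its only design calculation, the power table in SAP 7.2.2, is not in dispute and does not depend on it.

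**1. Is the term absent?** Reading SAP 7.1.2 line by line against SAP 5.4 and Protocol 8.3, every setting, length-of-stay, severity and discharge item refers to the most recent or previous stroke. None refers to the day the anticoagulant was started. One bullet in the list is blank in the readable text, so this finding is limited to what can be read.

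**2. Does another step adjust for it?** The Cox model in Protocol 8.7 has treatment only. The summary table in SAP 7.2.3 points the Cox rows to section 5.4, but even if that means added covariates, section 5.4 has no start setting. SAP 4.4 plans no subgroups.

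**3. How large could the effect be?** Treat in-hospital start as a binary confounder. Let pA and pW be its shares in the weighted apixaban and warfarin cohorts, and H its residual hazard ratio for a recorded event, given the other covariates. With uncommon events, the observed hazard ratio is approximately the true one multiplied by

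B = [1 + pA(H − 1)] / [1 + pW(H − 1)].

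The shares 45% and 60%, and every value of H, are assumptions. The hazard ratio of 0.65 is the expected value in SAP 7.2.2.

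| pA | pW | H | B | 0.65 × B |
|---|---|---|---|---|
| 0.45 | 0.60 | 1.5 | 1.225/1.300 = 0.94 | 0.61 |
| 0.45 | 0.60 | 2.0 | 1.450/1.600 = 0.91 | 0.59 |
| 0.60 | 0.45 | 1.5 | 1.300/1.225 = 1.06 | 0.69 |
| 0.60 | 0.45 | 2.0 | 1.600/1.450 = 1.10 | 0.72 |
| 0.45 | 0.60 | 0.8 | 0.910/0.880 = 1.03 | 0.67 |

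A wider assumption, 30% against 50% with H from 1.25 to 3.0, gives B from 1.075/1.125 = 0.96 to 1.6/2.0 = 0.80 when warfarin has the higher share (0.65 becomes 0.62 to 0.52). With the shares reversed, B runs from 1.05 to 1.25 (0.65 becomes 0.68 to 0.81).

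**4. Could H be below 1?** Yes. Time on the ward after the start adds follow-up in which no stroke or major bleed can count. The longest stay allowed by SAP exclusion 5 is 6 months and maximum follow-up is 24 months. As an outer case, a patient followed for the full period could lose up to 6/24 = 25% of follow-up in this way. Whether this outweighs a worse prognosis cannot be told from the documents.

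**5. Would the planned balance check show it?** Only if the variable is in the table. Shares of 45% and 60% give a standardised difference of 0.15/√[(0.45×0.55 + 0.60×0.40)/2] = 0.15/0.494 = 0.30, three times the SAP threshold of 0.1.

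**The case against.** **Partial proxies exist.** For a start during the stroke admission itself, the treatment status, severity scales, length of stay, discharge destination and thrombolysis items describe that admission. Heart failure, heparins, anti-arrhythmics and cardioversion carry some information on other acute stays. Two patients who share one covariate value therefore do not share one propensity score. This stands and narrows the gap, mainly to starts during admissions not due to stroke. No listed item identifies those starts.

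**Protocol exclusion 5 may remove many ward starters.** This also stands. The protocol and SAP wordings differ, and the extent of the problem depends on which one is applied.

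**Residual confounding is acknowledged.** Protocol 8.9 says so, and SAP 7.2.1 plans E-values. For a hazard ratio of 0.65 the E-value is 1.538 + √(1.538 × 0.538) = 2.45. That describes how strong an unmeasured confounder would have to be. It does not replace adjustment for one that can be derived.

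**A stronger reading about department.** A reader might infer that the plan says specialty drives drug choice, so that prescribing department must also enter the model. The documents do not support this. SAP 2.2 says only "Although neurologists generally use direct oral anticoagulants (DOAC) for secondary prevention", a background remark about a drug class and one specialty, with no comparison of departments and no separate mention of apixaban. The entry "Table2. Categories of clinical departments" in Protocol 13 has no matching table or variable in the readable text, and nothing says that the extract holds department. If department affects drug choice but not outcome, adjusting for it adds variance and removes no bias.

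**Conclusion.** The omission is confirmed in the readable text, and the point holds for care setting at the start of the anticoagulant. It can confound both primary hazard ratios if the drugs differ in their share of in-hospital starts, and no other planned step removes that. Under the 45%/60% assumption with H of 1.5 to 2.0, the distortion is about 6% to 10% in either direction.

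A reader might infer that the bias favours apixaban. The documents give no share of in-hospital starts and no association with outcome, and the endpoint rules could put H on either side of 1, so the sign is unknown. The stroke counting rule in SAP 5.1.1 is worded for stroke; how it applies to the systemic embolism component is not spelled out.

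This is an avoidable weakness that should be corrected before analysis. It is not a flaw that invalidates the design.

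**What to change.** In SAP 7.1.2, add to the propensity score the care setting on the date of the first warfarin or apixaban prescription, in three categories: inpatient for stroke, inpatient for another reason, outpatient. Tie it to the prescription date, because Protocol 8.1.1.1 places the index date one day later. Show the variable before and after weighting in the balance table, against the same 0.1 threshold.

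Reconcile exclusion 5 in Protocol 8.2.2 with exclusion 5 in SAP 4.1.2, so that it is clear which in-hospital starters are in the cohort.

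Prescribing department need not enter the model. If the extract holds it, it can be described in the balance table.

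The cost is a few lines of SAP text, one variable derived from linked claims and a few table rows. If setting strongly predicts drug choice, the weights may become slightly more variable.

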8.1.1.1. Index date

The next day of the day when patients diagnosed NVAF initiate warfarin or apixaban

8.1.1.2. stroke

8.1.1.3. Defined using pre-designated ICD-10 codes (see Statistical Analysis Plan). Ischemic and hemorrhagic stroke will be included,stroke

Stroke is defined using predefined ICD-10 codes and if hospitalization for the treatment of the stroke is necessary, it will be regarded as stroke incident during the followup period.
(applicable only to the outpatients when recurrent stroke occurs)

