### 4. ANALYSIS SETS/POPULATIONS

#### 4.1. FULL ANALYSIS SET

##### 4.1.1. Inclusion criteria

*Patients must meet all the following selection criteria*

1. *Patients registered in the MDV database 2008 through 2021.*
2. *Patients newly diagnosed with non-valvular atrial fibrillation*
3. *Patients who started anticoagulation treatment with either warfarin or apixaban after diagnosis of NVAF*
4. *Age 20 years or older on the index date*
5. *Patients who have a history\* of stroke (cerebral infarction, cardioembolic stroke, or hemorrhagic stroke) or TIA before the index date are inclusion criteria only for secondary prevention cohort, otherwise patients will be included in the primary prevention cohort.*

\* A history of stroke is checked as far back as possible from the INDEX DATE to see if there is a history of stroke. That is, the period is from the date each patient first appeared in the MDV database to the day before the index date.

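### Time from the qualifying stroke or TIA to index is not among the readable propensity covariates, so a difference between arms in stroke recency would be neither directly balanced nor shown

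*SAP*

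**What the plan says.** **Window.** For prior stroke or TIA, SAP 4.1.1 states "the period is from the date each patient first appeared in the MDV database to the day before the index date". No minimum or maximum interval is set. The database criterion is "Patients registered in the MDV database 2008 through 2021", and Protocol 8.1.1.1 defines index as "The next day of the day when patients diagnosed NVAF initiate warfarin or apixaban".

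**Covariates.** SAP 7.1.2 lists eight features of the latest event: treatment setting, mRS, JCS, ADL, length of stay, discharge destination, thrombolysis and type. Where a patient has had several events, "only information regarding most recent stroke (i.e., stroke event closest to the index date) will be used". Neither the date of the event nor the interval to index appears there, in the SAP 5.4 table or in Protocol Table 1. An empty bullet stands between the stroke-type item and the note on multiple events.

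**Later steps.** Protocol 8.7 specifies a "Cox proportional hazards regression model that incorporate only the index OACs as independent variables". The summary table in SAP 7.2.3 instead refers the Cox models to section 5.4 for covariates. SAP 4.4 plans no subgroups. The only sensitivity analysis is the E-value (SAP 7.2.1).

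**Related exclusion.** SAP exclusion 5 removes "Patients who were hospitalized for more than 6 months (including index date) regardless of reason for hospitalization". Protocol exclusion 5 removes patients in continuous hospital care for a first stroke or other serious disease, and gives no duration.

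**The concern.** The secondary prevention cohort can combine patients who start an anticoagulant shortly after a stroke with patients whose stroke was many years earlier. If recency affects recurrence or bleeding, and also affects which drug is started, it confounds both primary hazard ratios. That risk falls with time since stroke is subject-matter judgement; the documents do not quantify it. On drug choice they say only that neurologists generally use DOACs while many patients remain on warfarin. A link between that choice and recency is an inference.

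The plan also treats time unevenly. All medicines and most comorbidities in the propensity list are restricted to a baseline of at most six months, but the stroke features have no window. A severity score from an old admission therefore enters exactly like one from last week. Unlike the vital signs and laboratory values that Protocol 8.9 names as unavailable, recency can largely be derived from dated claims.

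**Working it through.** **1. Range of the interval.** Index is the day after drug start, and the search runs to the day before index. An event on the day of drug start therefore qualifies, one day before index. The database runs from 2008 to 2021, so the upper end is about 2021 − 2008 = 13 years.

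**2. The plan's own figures.** The documents give no figure on recency. The nearest is the power table in SAP 7.2.2. At HR 0.6 and 1.2%/year, the Schoenfeld formula needs 4 × (1.960 + 0.842)² / (ln 0.6)² = 121 events. Two-year event probabilities are 1 − exp(−0.024) = 0.0237 and 1 − exp(−0.0144) = 0.0143. Then 121 / 0.0380 gives 3,184 per group, against 3,166 stated. All 12 cells agree within 1.3%. At HR 0.65, with 15,000 patients split 1:1, 1.2%/year and full two-year follow-up, about 294 events are expected and power is about 96%. The issue is bias, not precision.

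**3. Bias formula.** Let *k* be the rate ratio for recent against remote events, and *p* the share of recent events in an arm after weighting. The mean rate in an arm is proportional to 1 + (k − 1)p, so

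observed HR ≈ true HR × [1 + (k − 1)p_apixaban] / [1 + (k − 1)p_warfarin].

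The true HR of 0.65 is the SAP 7.2.2 expectation. Both *k* and *p* are assumptions. Example: k = 2 with 45% v 50% gives 1.45/1.50 = 0.967, and 0.65 × 0.967 = 0.63.

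| k | 45% v 50% | 50% v 45% | 40% v 60% | 60% v 40% |
|---|---|---|---|---|
| 1.5 | 0.64 | 0.66 | 0.60 | 0.70 |
| 2 | 0.63 | 0.67 | 0.57 | 0.74 |
| 3 | 0.62 | 0.68 | 0.53 | 0.79 |

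(Columns: recent share on apixaban v warfarin.)

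**4. Against the plan's balance criterion.** For 45% v 50%, the standardized difference is 0.05 / √[(0.45×0.55 + 0.50×0.50)/2] = 0.10, which is the SAP threshold. For 40% v 60% it is 0.20 / √0.24 = 0.41. Even the larger value would go unseen, because an unlisted variable has no row in the balance table.

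**5. Can a later step correct it?** The two descriptions of the Cox model conflict: drug only (Protocol 8.7), or covariates from section 5.4 (SAP 7.2.3). Section 5.4 lacks the interval, so neither version adjusts for it.

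**The case against.** **The empty bullet.** It sits where another stroke covariate would be expected, and text lost in conversion is not missing from the plan. This stands. If the interval was listed there, the point is closed once the sponsor confirms it.

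**Early events are partly removed.** SAP 5.1.1 counts a recurrence only after discharge and readmission, SAP 5.2.1 leaves out bleeding during a hospital stay, and Protocol exclusion 5 may remove patients still in their first stroke admission. This stands in part. The rules thin out the earliest period for inpatients, but none separates a stroke last month from one years ago. The SAP version of exclusion 5 is also looser than the Protocol's.

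**The arithmetic holds k constant.** Follow-up lasts up to two years, and if risk falls with time the average *k* is smaller. This stands. The 20-point columns also need a residual standardized difference of about 0.4, for which the documents offer no support.

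**Proxies and the E-value.** Treatment setting, length of stay, discharge destination, thrombolysis, type, and baseline heparin and antiplatelet use would absorb part of any imbalance. The E-value addresses unmeasured confounding: at 0.65 it is 1.54 + √(1.54 × 0.54) = 2.45, treating the hazard ratio as a risk ratio. The proxies are a real mitigation. The E-value says how strong a confounder would have to be, but it removes no bias and should not stand in for a variable that can be derived.

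**A stronger reading.** A reader might infer that the arms do differ in recency, or that the primary results are biased in apixaban's favour. The documents contain no timing data by drug and support neither inference.

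**Conclusion.** The gap is real on the readable text: the qualifying event has no interval limit, and no listed covariate records the interval. A difference between arms would be balanced only through proxies and would not be displayed. Size and direction are unknown. Under an assumed *k* of 1.5 to 3, a five-point residual difference moves 0.65 to 0.64-0.62, or to 0.66-0.68 if reversed. The span from 0.53 to 0.79 is an extreme, requiring a 20-point residual difference and, at its ends, a threefold rate sustained throughout follow-up. The conclusion depends on the empty bullet having held no such item. The power table is unaffected. This is a worthwhile, inexpensive improvement, not evidence that the planned comparison is invalid.

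**What to change.** 1. Confirm whether an item was lost at the empty bullet in SAP 7.1.2.
2. If not, add time from the most recent stroke or TIA to index, as categories or a spline, to the propensity covariates in SAP 7.1.2 and to the SAP 5.4 table.
3. Report its standardized difference before and after weighting.
4. Give events that cannot be dated a separate unknown-timing category.
5. Reconcile Protocol exclusion 5 with SAP exclusion 5, since they affect how many very recent strokes enter the cohort.

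The cost is one derived variable, a few extra model terms and SAP wording; the reconciliation may also touch the Protocol. Where a diagnosis has been carried over in the claims, the derived interval will be misclassified for some patients, which limits the benefit but does not remove it.
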